10.2 Sample Size Considerations

The study will randomize 80 adults infected with one of the endemic mycoses living in the United States, Canada and Central/South America (40 Histo, 20 Cocci, 20 other endemic mycoses). This sample size provides adequate power (77%) to reject the null hypothesis of equal pharmacokinetic means when the population mean difference is $\mu 1$ - $\mu 2$ = 231.7 - 291.7 = -60.0 with standard deviations of 94.0 and 101.8 for the study groups, and with a significance level (alpha) of 0.050 using a two-sided two-sample unequal-variance t-test.

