4 STUDY DESIGN

This is a prospective, multi-center, randomized, open-label parallel arm study involving patients with proven or probable invasive endemic fungal infection to ascertain the pharmacokinetics, safety, efficacy, and tolerability of oral SUBA-itraconazole or itraconazole. Patients will receive randomized open-label study drug (either SUBA-itraconazole 65 mg twice daily or itraconazole 100 mg twice daily) over a 42-day period and then continue on their assigned open-label therapy until day 180.

The study sample size will be 80 evaluable patients – target enrollment to include approximately 40 histoplasmosis, 20 coccidioidomycosis, and 20 other endemic fungal infections.

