5.3 Treatment Assignment Procedures

5.3.1 Randomization Procedures

Stratified randomization will be used to assign qualifying participants to either conventional itraconazole or SUBA-itraconazole and dosed according to HIV status (positive or negative by clinical self-report) (Section 6.2).

Randomization procedures are described in the Manual of Procedures.

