10.3 Study Outcomes

Stage I- Randomized Open-Label, Parallel Group

Primary Endpoints

- 1. Pharmacokinetic superiority at Day 14
 - a) Inter- and intra- patient variability: Time to attain therapeutic plasma concentrations of itraconazole (> 500 mcg/L)
 - b) Interpatient variability as calculated by co-efficient of variation

Trough (pre-morning dose) sample will be collected at Days 14 and 42. Using validated LC-MS/MS methods, blood samples will be analyzed to quantify plasma concentrations of itraconazole and hydroxyitraconazole.

Participants should arrive to the trial site having **not** taken their morning dose of study drug.

Note: site investigators are discouraged from drawing independent PK laboratories to check itraconazole levels outside of the designated timepoints (Day 14)

2. Tolerability - ability to remain on study drug at Day 42 with less than a 7-day interruption of therapy

Secondary Endpoints

- PK at day 7 plasma concentrations of itraconazole- (comparative trough, steady state plasma itraconazole concentrations of SUBA-itraconazole 65mg capsules with food to itraconazole 100mg capsules with food over 7 days)
- 2. PK at day 42 plasma concentrations of itraconazole- (comparative trough, steady state plasma itraconazole concentrations of SUBA-itraconazole 65mg capsules with food to itraconazole 100mg capsules with food over 42 days)
- 3. Efficacy: clinical outcomes (time to relief of fungal signs and symptoms) at days 14, 28, and 42
- 4. Safety- defined as: adverse events that occurred in each study arm by Day 42
- 5. Tolerability ability to remain on study drug at Days 14 & 28
- 6. Days of Hospitalization and ICU stays at Day 42
- 7. Other health economic endpoints:
 - 1. Number of unscheduled procedures (i.e., labs, scans, etc.) at Day 42
 - 2. Total number of capsules taken at Day 42
 - 3. SF-20 (QOL) assessments at Day 42

Stage II- Open-Label, Extension

Primary Endpoint

- 1. Efficacy- Free from proven or probable invasive endemic fungal infection at Day 180
- 2. Tolerability- ability to stay on study drugs at Days 43 180.

Secondary Endpoints

- 1. Safety- Adverse events that occurred in each study arm between Days 43 180 or end of therapy
- 2. Days of Hospitalization (Days 1 180) defined as days of hospitalization and ICU stays from randomization to Day 180 or end of therapy)

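### The 77% power in Section 10.2 is for an unlabelled difference in means, not for primary endpoint 1(a); if those means are itraconazole troughs in mcg/L, few patients would pass the 500 mcg/L threshold

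*Combined protocol and SAP*

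**What the plan says.** Section 10.2 sets the sample size: "The study will randomize 80 adults infected with one of the endemic mycoses". It continues: "This sample size provides adequate power (77%) to reject the null hypothesis of equal pharmacokinetic means", for a difference of "231.7 - 291.7 = -60.0 with standard deviations of 94.0 and 101.8 for the study groups", at a "significance level (alpha) of 0.050 using a two-sided two-sample unequal-variance t-test". It gives no unit, analyte, sampling day, regimen or source for these values, and it does not say which mean belongs to which arm.

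Section 10.1 names a t-test for Day 14 PK without naming the variable to be tested. Section 10.3 lists two components under Day 14 PK superiority. Component 1(a) is "Time to attain therapeutic plasma concentrations of itraconazole (> 500 mcg/L", and 1(b) is a coefficient of variation between patients. A comparison of trough concentrations is listed only as a secondary endpoint, at Days 7 and 42. A Day 14 comparison of means is not listed.

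Section 6.3 also uses 500 ng/mL, which is numerically the same as 500 mcg/L, but for itraconazole plus hydroxyitraconazole. On regimen, Section 4 gives one capsule strength twice daily in each arm (65 mg or 100 mg). Section 6.2 gives two capsules twice daily, after a three-times-daily phase on Days 1 to 3.

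**The concern.** The power statement and the listed primary endpoint describe different quantities, and nothing in the documents links them. There are two possibilities, and each leaves a gap.

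- **The planning means are Day 14 itraconazole troughs in mcg/L.** Both then sit well under the threshold in 1(a). The trial would make its PK superiority claim partly on a time-to-threshold that most patients may never reach.
- **The planning means are something else**, such as an AUC, another analyte, another unit or another regimen. The 77% is then not shown to apply to this trial. The difference between Sections 4 and 6.2 makes this possibility hard to rule out.

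At stake is whether the primary PK endpoint, as written, can answer the superiority question, and whether its stated power can be relied on.

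**Working it through.** **Inputs.** From Section 10.2: N = 80, means 231.7 and 291.7, SDs 94.0 and 101.8, two-sided alpha 0.05, unequal-variance t-test. From Section 10.3: threshold 500 mcg/L. Assumed: 40 per arm with every patient contributing a value, since Section 5.3.1 describes stratified randomization without giving a ratio.

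**1. The plan's own figure.**

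SE = √(94.0²/40 + 101.8²/40) = √(220.90 + 259.08) = 21.91.

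Noncentrality = 60.0/21.91 = 2.739, with Satterthwaite df = 77.5.

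Power from the noncentral t distribution = **77.2%** (normal approximation 78.2%). The stated 77% reproduces. It depends only on the difference, the SDs and the group sizes; 500 does not enter.

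**2. Distance from the threshold, if the values are itraconazole troughs in mcg/L (assumption).**

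- 231.7/500 = 46%; (500 − 231.7)/94.0 = 2.85 SDs below.
- 291.7/500 = 58%; (500 − 291.7)/101.8 = 2.05 SDs below.

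**3. Expected share above 500 at a single draw.** The gamma and log-normal rows use the same mean and SD. For the log-normal, σ² = ln(1 + SD²/mean²) and μ = ln(mean) − σ²/2. The last row is the one-sided Chebyshev (Cantelli) bound, SD²/(SD² + (500 − mean)²), which needs no assumption about shape.

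| Shape | Mean 231.7 | Mean 291.7 | Patients, 40 + 40 |
|---|---|---|---|
| Normal | 0.2% | 2.0% | 0.09 + 0.81 = 0.9 |
| Gamma | 1.1% | 3.5% | 0.43 + 1.41 = 1.8 |
| Log-normal | 1.5% | 3.9% | 0.61 + 1.57 = 2.2 |
| Any shape (ceiling) | 10.9% | 19.3% | 4.4 + 7.7 = 12.1 |

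**4. What this leaves for endpoint 1(a).** With so few patients above 500, a comparison of times is little more than a comparison of who got there.

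- Fisher exact power on the single-draw shares, by enumeration at 40 versus 40, is 0.01% (normal) and 0.25% (log-normal), so below 0.3% in both cases.
- The chance that none of 80 exceeds 500 is (1 − 0.0022)⁴⁰ × (1 − 0.0204)⁴⁰ ≈ 40% (normal), or about 11% (log-normal).

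**5. Two draws instead of one.** Appendix A has PK draws on Days 7 and 14. If both had the log-normal shares (assumption), the share ever exceeding 500 could be at most 2 × 1.52% = 3.0% and 2 × 3.93% = 7.9%. That is about 1.2 and 3.1 of 40.

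**6. If the values are another measure or regimen.** Steps 2 to 5 do not apply. Step 1 then gives the power for a quantity that the documents do not tie to this trial.

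**The case against.** The strongest reply is that the trough-in-mcg/L reading is an assumption. Section 10.2 gives no unit, so if the values are an AUC, comparing them with 500 means nothing. That stands, and the figures in steps 2 to 5 are conditional on it. It does not rescue the power statement, because the other reading leaves the 77% unconnected to this trial's endpoint.

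A second reply is that Section 10.1 names a t-test and Section 10.2 powers means, so a mean comparison is plainly intended. This is a fair reading of intent, and the fix follows it. But Section 10.3 does not list that comparison as primary, and it does list the threshold endpoint.

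Third, two draws and the three-times-daily phase on Days 1 to 3 could raise attainment. They could. Step 5 shows that the second draw alone leaves events sparse under a log-normal shape, and the documents give no figures for the effect of the early phase.

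Some stronger readings are tempting but not supported:

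- A reader might infer that the planning values and the threshold contradict each other. They do not: a plan may expect means below a threshold it names, and Section 6.3 provides for patients with combined levels under 500 ng/mL.
- A reader might infer that 1(a) would have no events at all. The expected count is about 1 to 2 of 80, and the distribution-free ceilings are higher.
- A reader might suspect a calculation error in the 77%. There is none.
- A reader might rescale the means by the number of capsules. The documents give no relation between dose and concentration that would justify this.

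**Conclusion.** The concern holds as a mismatch between the powered quantity and the listed primary endpoint. The 77% is correct for the difference in means it describes, assuming 40 per arm, and is not the power of endpoint 1(a).

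If the means are itraconazole troughs in mcg/L, 1(a) would rest on very few events: 0.2-1.5% and 2.0-3.9% of patients at one draw under the usual shapes. Even at the distribution-free ceilings (10.9% and 19.3%), most patients would be below 500 at that draw. If the means are something else, the plan has not shown what power this trial has for its primary PK comparison. The documents do not settle which case applies, but both call for a change to the text.

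**What to change.** - **Section 10.3:** make the continuous Day 14 itraconazole trough the primary PK variable, tested by the t-test already named in Section 10.1. Report the share of patients above 500 mcg/L at Day 14 descriptively.
- **Section 10.2:** confirm that all four planning values are Day 14 itraconazole troughs under the trial's regimen, and state the unit and source. If they are not, replace them and restate the power.
- **Sections 4 and 6.2:** reconcile the two descriptions of the regimen, so that the planning values can be tied to one of them.

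The cost is a check on the source of four numbers and a rewording of Sections 10.2 and 10.3. The threshold endpoint gives up its confirmatory role, and the stated power may change if the planning values have to be replaced.

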10.3 Study Outcomes

Stage I- Randomized Open-Label, Parallel Group

Primary Endpoints

- 1. Pharmacokinetic superiority at Day 14
 - a) Inter- and intra- patient variability: Time to attain therapeutic plasma concentrations of itraconazole (> 500 mcg/L)
 - b) Interpatient variability as calculated by co-efficient of variation

Trough (pre-morning dose) sample will be collected at Days 14 and 42. Using validated LC-MS/MS methods, blood samples will be analyzed to quantify plasma concentrations of itraconazole and hydroxyitraconazole.

Participants should arrive to the trial site having **not** taken their morning dose of study drug.

Note: site investigators are discouraged from drawing independent PK laboratories to check itraconazole levels outside of the designated timepoints (Day 14)

2. Tolerability - ability to remain on study drug at Day 42 with less than a 7-day interruption of therapy

Secondary Endpoints

- PK at day 7 plasma concentrations of itraconazole- (comparative trough, steady state plasma itraconazole concentrations of SUBA-itraconazole 65mg capsules with food to itraconazole 100mg capsules with food over 7 days)
- 2. PK at day 42 plasma concentrations of itraconazole- (comparative trough, steady state plasma itraconazole concentrations of SUBA-itraconazole 65mg capsules with food to itraconazole 100mg capsules with food over 42 days)
- 3. Efficacy: clinical outcomes (time to relief of fungal signs and symptoms) at days 14, 28, and 42
- 4. Safety- defined as: adverse events that occurred in each study arm by Day 42
- 5. Tolerability ability to remain on study drug at Days 14 & 28
- 6. Days of Hospitalization and ICU stays at Day 42
- 7. Other health economic endpoints:
 - 1. Number of unscheduled procedures (i.e., labs, scans, etc.) at Day 42
 - 2. Total number of capsules taken at Day 42
 - 3. SF-20 (QOL) assessments at Day 42

Stage II- Open-Label, Extension

Primary Endpoint

- 1. Efficacy- Free from proven or probable invasive endemic fungal infection at Day 180
- 2. Tolerability- ability to stay on study drugs at Days 43 180.

Secondary Endpoints

- 1. Safety- Adverse events that occurred in each study arm between Days 43 180 or end of therapy
- 2. Days of Hospitalization (Days 1 180) defined as days of hospitalization and ICU stays from randomization to Day 180 or end of therapy)

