6.3 Modification of Study Intervention/Investigational Product for a Participant

Dose increase, reduction or cessation is permitted at the discretion of the investigator. Any modification to the dosing regimen will be noted in the source document and entered into the eCRF.

The Investigator will consider a dose modification For the following combined drug levels (itraconazole + hydroxyitraconazole) at Day 14 and Day 42:

- <500ng/ml increase dose

- >5000ng/ml decrease dose

Any modification to the dosing regimen should have blood-levels re-analyzed every two weeks until the target therapeutic level is achieved (see schema below).

The Investigator will consider dose reduction and/or dose cessation for toxicity if the participant:

- Develops a study drug-related, grade 4 adverse event
- Develops a study drug-related, serious adverse event (SAE)
- Develops dose-limiting study drug-related toxicity despite dose-reduction.

6.4 Accountability and Assessment of Subject Compliance with Study Intervention/Investigational Product

Study drug accountability procedures will be performed by the clinical site. The site will maintain all product per storage guidelines highlighted in the product insert or IB. The clinical site will document receipt, dispensing, and any unused product. This documentation will be maintained throughout the conduct of the study.

Study drug compliance will be assessed at each visit (Day 7, Day 14, Day 28, Day 42, Day 84, Day 180). Subjects will bring all containers and unused medication (if applicable) to each visit. Sites will determine the total amount of product dispensed and compare it to returned product. This information will be collected on the source documents and entered into the eCRF.

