10 STATISTICAL CONSIDERATIONS

10.1 Study Hypotheses and Statistical Analyses

For the primary outcomes of Stage I, t- and chi-square tests will be used to test whether the treatment group experiences superior PK at Day 14 and Tolerability at Day 42, respectively. If it is determined that the assumptions of the t-test are not met by the data, non-parametric statistical tests will be employed; Fisher's exact test will be used as deemed necessary. In the unusual occurrence that the study groups are not in equipoise with respect to the measured baseline demographic, behavioral and clinical characteristics, linear and logistic regression models will be used to compare the treatment groups, adjusted for any observed differences. The same aforementioned statistics techniques will be used for the secondary outcomes of Stage I as well as the primary and secondary outcomes of Stage II.

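### The Day 14 primary PK endpoint in section 10.3 (time to >500 mcg/L and inter-patient CV) is not linked in the text to the t-test in 10.1 or the 77% power in 10.2

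*Combined protocol and SAP*

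**What the plan says.** - **Endpoint (section 10.3, Stage I primary).** Under the label "Pharmacokinetic superiority at Day 14" there are two items: (a) "Time to attain therapeutic plasma concentrations of itraconazole (> 500 mcg/L"), and (b) "Interpatient variability as calculated by co-efficient of variation". Trough comparisons appear only among the secondary endpoints, at Day 7 ("PK at day 7 plasma concentrations of itraconazole", described there as a comparison of steady-state troughs) and in the same form at Day 42.
- **Test (section 10.1).** The plan states that "t- and chi-square tests will be used to test whether the treatment group experiences superior PK at Day 14"; the word order pairs the t-test with PK and the chi-square test with tolerability. If the t-test assumptions fail, "non-parametric statistical tests will be employed", none of them named. Fisher's exact test is to be used where judged necessary, and linear or logistic regression if the arms differ at baseline.
- **Power (section 10.2).** The trial has 77% power to "reject the null hypothesis of equal pharmacokinetic means", with means 231.7 and 291.7, SDs 94.0 and 101.8, and a two-sided unequal-variance t-test at 0.05. No analyte, unit, time point, arm label or source is given.
- **Sampling.** The collection sentence in 10.3 lists troughs at Days 14 and 42. Day 7 comes from the secondary endpoint, section 7.3 and Appendix A. Each of these visits has a window of +/- 3 days, and 10.3 discourages PK levels at other times.

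**The concern.** A primary endpoint, its test and its power should refer to the same variable. Here the endpoint is a time and a CV, the test compares means, and the power is for the means of a variable that is not named. If this stays, the variable and the test for a primary outcome of an open-label trial have to be chosen at analysis, possibly after levels by arm are known. The 77% could then be quoted for whichever endpoint is chosen, although nothing in the documents shows that it covers that endpoint.

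**Working it through.** **1. Reproduce the 77%.** Inputs from 10.2: difference 60.0, SDs 94.0 and 101.8, two-sided 0.05, 80 patients. The allocation ratio is not stated, so I assume 1:1, 40 per arm.

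- Standard error = sqrt(94.0²/40 + 101.8²/40) = sqrt(220.90 + 259.08) = 21.91.
- Noncentrality = 60.0/21.91 = 2.739; Satterthwaite df = 77.5; critical t = 1.991.
- Power from the noncentral t = 77.2%. A 40,000-run simulation gives 77.5%.

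The stated figure is right, for a Welch comparison of two means.

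**2. Item (b), the CV.** A CV is one number per arm. The t-test on patient values asks whether the means differ; two arms with equal means can have different CVs, and the reverse. Chi-square and Fisher's exact tests compare proportions. Linear and logistic regression compare means and odds. The non-parametric fallback names no test and is triggered by failed t-test assumptions, so it does not supply a CV comparison. Section 10.1 therefore has no test for (b).

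**3. Item (a), time to >500 mcg/L.** Up to Day 14 there are at most two scheduled troughs, at Days 7 and 14. Each patient can be seen only as:

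- above 500 by Day 7;
- first above 500 between Days 7 and 14;
- not above 500 by Day 14.

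This is an ordered three-category outcome, or equivalently an interval-censored time. A t-test on scores for the categories would not compare elapsed times. A rank test would suit the ordering, and Fisher's exact test would suit attained or not by Day 14, at the price of ignoring timing. Section 10.1 assigns neither to (a).

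**4. Combining (a) and (b).** No section says whether superiority needs both items, either one, or some ordering of the two.

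**5. What the 77% covers.** Because 10.2 does not identify its variable, the figure cannot be tied to (a) or to (b).

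**6. Illustration only: the CV.** Suppose that the 10.2 variable were the one whose CV is compared, and that it is lognormal.

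- CVs: 94.0/231.7 = 40.6% and 101.8/291.7 = 34.9%.
- Log-scale variances, ln(1 + CV²): 0.1524 and 0.1149; ratio 1.326.
- Two-sided F-test at 0.05 with 39 and 39 df: upper critical value 1.891. Power = P(F > 1.891/1.326) + P(F < 1/(1.891 × 1.326)) = 0.136 + 0.003 = about 14%.
- A different method, a z-test on the log ratio of the CVs, gives about 13%.

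So power for means does not carry over to a contrast of CVs, even when both are computed from the same planning values.

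**The case against.** The strongest reply is that a Day 14 trough comparison was plainly meant. The outcome is headed as PK at Day 14, a Day 14 trough is collected, and a comparison of mean troughs would fit both 10.1 and 10.2. That reading is plausible, so the sections cannot be called impossible to link. But 10.3 shows how its authors write a trough endpoint, at Days 7 and 42, and it does not write Day 14 that way. If a trough was meant, the text still has to say so.

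The second reply is that 10.1 has tools for attainment. This stands: a rank test or Fisher's exact test would be valid. Nor would a t-test on category scores inflate the error rate: with assumed shares of 50/30/20% in both arms scored 7/14/21, its type I error is 0.050 at 40 per arm. For (a), what remains is that no test is assigned and the scoring is not stated.

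A reader might also infer three stronger things that the documents do not support:

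- **That the trial has only 14% power for its primary PK endpoint.** That figure assumes what the 10.2 variable is. It does not measure this trial.
- **That few patients could reach the threshold, because 231.7 and 291.7 lie below 500.** Section 10.2 gives no unit and no analyte, so the numbers cannot be set against 500 mcg/L.
- **That the endpoint's analyte is open, because section 6.3 uses "combined drug levels (itraconazole + hydroxyitraconazole) at Day 14 and Day 42".** That is a trigger for considering dose changes. Section 10.3 names itraconazole for item (a) and for the secondary trough endpoints. Only the silence in 10.2 counts.

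**Conclusion.** The concern holds as a mismatch between sections, and it needs correcting because it affects a primary outcome. Item (b) has no test; item (a) has usable tests but none assigned; no rule combines them; and the 77% belongs to a comparison of means that 10.3 does not list as primary. A reader might infer that the sample size calculation is wrong. It is not: 77.2% reproduces it, given 1:1 allocation. Apart from that figure, the conclusion rests on the text of 10.1 to 10.3 and the sampling schedule, and it does not depend on the CV illustration.

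One matter should be kept separate. Section 4 speaks of 80 evaluable patients and 10.2 of randomizing 80, with no allowance for loss. The same Welch calculation gives 73% with 72 results and 67% with 64 (losses assumed). That is a question about the sample size, not about which endpoint it serves.

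**What to change.** Make 10.1, 10.2 and 10.3 agree by amendment before any by-arm review of PK levels. Waiting until just before the analysis is too late: the trial is open-label and section 6.3 has investigators act on Day 14 levels. If levels have already been seen by arm, disclose that with the change. The choice between two options is the sponsor's.

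- **(i) Trough as primary.** Only if the source of the 10.2 figures confirms that they are Day 14 itraconazole troughs: name the per-patient pre-morning-dose itraconazole trough at Day 14 (+/- 3 days) as the primary PK endpoint, tested by the two-sided unequal-variance t-test at 0.05 as in 10.2. Make attainment of >500 mcg/L and the inter-patient CV supportive.
- **(ii) Keep both listed items as primary.** Analyse attainment as the ordered three-category outcome with a named rank test, or as interval-censored time. Name a test for CVs or log-scale variances, state how the two results combine, and replace the 77% with power for those tests.

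Under either option, state in 10.2 the analyte, unit, time point and arm for 231.7 and 291.7, and quote the 77% only for the comparison of means.

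The cost is a text amendment, IRB/IEC approval before use (section 13.2) and an update to the trial registration. No new samples are needed, since Days 7 and 14 are already in Appendix A. Option (i) needs no new patients but changes the listed primary items. Option (ii) needs planning values that the documents do not contain, and 40 per arm may prove few for a CV comparison.

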6.2 Dosage, Preparation and Administration of Study Intervention/Investigational Product

Study participants will be randomized to receive either open-label SUBA-Itraconazole or conventional itraconazole. Each treatment arm will be dosed as follows:

Arm A: Open-Label SUBA-itraconazole 65 mg Capsules – administered with food

Stage 1

- Day 1 3: two 65 mg capsules, three times daily
- Day 4 42: two 65 mg capsules, twice daily

Stage 2:

Day 43 – 180: two 65 mg capsules, twice daily.

Arm B: Conventional Itraconazole 100 mg Capsules – administered with food Stage 1:

- Day 1 3: two 100 mg capsules, three times daily
- Day 4 42: two 100 mg capsules, twice daily

Stage 2:

Day 43 – 180: two 100 mg capsules, twice daily).

Based on standard of care for invasive endemic fungal infection, some participants will be prescribed conventional itraconazole (non-study drug) after Day 180 for up to a year or beyond, as prescribed by their physician. Information for discounted itraconazole will be provided at the end of the study to help defray costs.

[figure not shown]

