7.3 Follow-up

Participants will be assessed in clinic at Day 7, Day 14, Day 28 (1 month), Day 42, Day 84 (3 months) and Day 180 (6 months). In the opinion of the investigator, clinic visits may be replaced with telemedicine visits or home visits, with allowances made for blood draws at remote or commercial laboratories. Documentation in source documents should clearly define accommodations in visit locations or methods when attempting to protect participants and other patients from potential exposure and hazards related to COVID-19. The Day 7, 14 and 42 visits allow a narrow window (+/- 3 days) so that accurate PK levels can be drawn.

The Day 84 and 180 visits will allow a window of (+/- 7 days).

At each visit, blood samples will be drawn for study-specific safety and efficacy labs. In addition a quality of life questionnaire will be administered at Day 42. See Appendix A for study procedures per visit.

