gBaseline Visit: Study drug is be started on Day 1. Visit windows for Day 7, 14 and 42 will be a +/-3 day window. All other visits have a +/- 7 day window.

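### The Day 7 PK window reaches back to Day 4, the morning the dosing frequency changes, so the secondary endpoint's steady-state trough can be drawn before any maintenance dose

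*Combined protocol and SAP*

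**What the plan says.** Section 10.3 defines Stage I secondary endpoint 1 as "comparative trough, steady state plasma itraconazole concentrations of SUBA-itraconazole 65mg capsules with food to itraconazole 100mg capsules with food over 7 days". Section 10.1 applies the methods of the primary outcomes to the secondary ones: a t-test, a non-parametric fallback, and regression if baseline characteristics are unbalanced. None of these takes account of the day on which the sample was drawn.

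On timing, section 7.3 says "The Day 7, 14 and 42 visits allow a narrow window (+/- 3 days) so that accurate PK levels can be drawn". Footnote g of Appendix A agrees: "Visit windows for Day 7, 14 and 42 will be a +/-3 day window". The same footnote fixes the day count: "Study drug is be started on Day 1".

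On dosing, section 6.2 gives Arm A "two 65 mg capsules, three times daily" on Days 1 to 3, then two capsules twice daily from Day 4. Arm B follows the same pattern with 100 mg capsules.

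Two gaps bear on the point. The sentence in 10.3 that defines the trough as a pre-morning-dose sample names Days 14 and 42 only. Section 4 describes twice-daily dosing over the 42 days, one capsule strength per dose, with no loading phase; it does not agree with 6.2.

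**The concern.** Section 7.3 justifies the window by the accuracy of the PK levels. At Day 7 its early edge falls on the morning when dosing frequency changes. A sample drawn then reflects the loading regimen alone, while one drawn on Day 10 reflects mostly maintenance dosing. Both enter the same comparison under one label.

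At stake is what the Day 7 result means. If it is reported as a steady-state comparison, readers will take it to describe the twice-daily regimens. Values from the first maintenance morning do not describe those regimens, and pooling them with later values adds spread that has nothing to do with formulation.

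**Working it through.** **1. The plan's own figure.** Section 10.2 gives means 231.7 and 291.7, SDs 94.0 and 101.8, two-sided alpha 0.05 and an unequal-variance t-test with 80 patients. Allocation is not stated; I assume 40 per arm.
- Standard error = √(94.0²/40 + 101.8²/40) = 21.91
- Noncentrality = 60.0/21.91 = 2.739, with 77.5 degrees of freedom
- Power = 77.2%. The stated 77% is reproduced.

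**2. Doses before the sample (exact, from 6.2, 7.3 and Appendix A).** Loading administrations: 3 days × 3 = 9. Maintenance administrations before a pre-morning sample on Day D: 2 × (D − 4).

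| Day | 4 | 5 | 6 | 7 | 8 | 9 | 10 |
|---|---|---|---|---|---|---|---|
| Maintenance administrations | 0 | 2 | 4 | 6 | 8 | 10 | 12 |

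The earliest Day 14 sample (Day 11) follows 2 × 7 = 14, so the problem is specific to Day 7.

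**3. Size at each day (assumed kinetics).** Assume linear one-compartment kinetics, rapid absorption, half-life h of 24 to 64 h and loading every 8 h. In units of one dose:
- Maintenance steady-state trough: S = a/(1 − a), with a = 2^(−12/h)
- Day 4 pre-dose level: L = b(1 − b⁹)/(1 − b), with b = 2^(−8/h)
- Ratio on Day 4: R(4) = L/S. Later days: R(D) = 1 + (R(4) − 1) × 2^(−24(D − 4)/h)

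For h = 24: S = 0.7071/0.2929 = 2.414; L = 0.7937 × 0.875/0.2063 = 3.366; R(4) = 1.39.
For h = 64: S = 0.8781/0.1219 = 7.205; L = 0.9170 × 0.5415/0.0830 = 5.983; R(4) = 0.83.

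| Half-life | Day 4 | Day 6 | Day 7 | Day 10 |
|---|---|---|---|---|
| 24 h | 1.39 | 1.10 | 1.05 | 1.01 |
| 36 h | 1.17 | 1.07 | 1.04 | 1.01 |
| 48 h | 1.00 | 1.00 | 1.00 | 1.00 |
| 64 h | 0.83 | 0.90 | 0.92 | 0.96 |

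Section 6.2 does not say that loading doses are 8 h apart. With meal-time loading (assumed at 0, 5 and 11 h) the 24 h ratio on Day 4 falls to 1.28 and the 36 h ratio to 1.11.

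**4. Effect on the comparison.** Borrow the 10.2 means and SDs for Day 7 and spread visits evenly over Days 4 to 10. The day-to-day multiplier then has a coefficient of variation c of 0 to 0.118 across 24 to 64 h. The inflated SD is √((1 + c²)(SD² + mean²) − mean²). At the worst case, c = 0.118:
- First group: √(1.0139 × (94.0² + 231.7²) − 231.7²) = 98.5
- Second group: √(1.0139 × (101.8² + 291.7²) − 291.7²) = 108.1
- Power = 73%. At 36 to 64 h it is 76 to 77%.

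**5. Discarding early samples.** Under the same even spread, excluding Days 4 and 5 leaves 40 × 5/7, about 29 per arm. The standard error becomes 25.73, the noncentrality 60.0/25.73 = 2.33 and power about 63%. Exclusion costs more than the variance that it removes.

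**6. If section 4 governed.** With no loading phase, a Day 4 sample follows 3 × 2 = 6 administrations, and its ratio to steady state is 1 − 2^(−72/h): 0.88 at 24 h and 0.54 at 64 h. Nothing would be mixed, but the steady-state label would still be unsupported.

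**The case against.** The best defence is that the effect is small and even-handed. Few visits need fall on the earliest day. The SDs in 10.2 already imply coefficients of variation of 94.0/231.7 = 41% and 101.8/291.7 = 35%, so an added 12% at most changes little. Loading pattern and window are the same in both arms; at a common half-life every day's multiplier is the same in both, and the ratio between arms is unchanged. At 48 h there is no shift at all. The endpoint is secondary, and section 6.3 ties dose modification to Day 14 and Day 42 levels, not to Day 7.

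Most of this stands. A reader might infer that the endpoint itself is shifted by −17% to +39%. The documents do not support that: the range applies to a single sample on the earliest permitted day, at the two ends of an assumed half-life range. A reader might also infer that the comparison of arms is biased. That needs visit timing or elimination to differ by arm, and the documents give no evidence of either, although an open-label comparison of two formulations does not rule it out.

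The defence does not reach the label. Nothing in the documents shows that steady state is reached within the permitted days, and nothing deals with a Day 4 sample.

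**Conclusion.** The point holds as a modest defect in one secondary endpoint. The calendar result is exact under 6.2: a compliant Day 4 sample follows 9 loading and 0 maintenance administrations. It takes the Day 7 sample to be pre-dose, which is the natural reading of a trough but is not stated for that day.

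The size is not fixed by the documents. It rests on assumed half-lives of 24 to 64 h, linear kinetics, 8-hourly loading, 40 per arm, evenly spread visits and 10.2 figures borrowed for a day to which the plan does not tie them. On those terms power is about 73 to 77% against 77%. The main consequences are some avoidable variance and a steady-state description that the plan does not support.

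It would be wrong to extend the point to the primary PK endpoint: the Day 14 window starts after 14 maintenance administrations.

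**What to change.** - Set the Day 7 PK window to −1/+3 days (Days 6 to 10) in section 7.3, the Appendix A column heading and footnote g.
- State in 10.3 that the Day 7 sample is also taken before the morning dose. Record the sampling day and the time since the last dose.
- Keep any sample drawn before Day 6 in the analysis with adjustment for sampling day. Add a sensitivity analysis restricted to Days 6 to 10.
- Remove the steady-state wording from secondary endpoint 1 unless pre-specified Day 7 to Day 14 trough ratios, in patients with no dose change, support it.
- Reconcile sections 4 and 6.2, which describe different regimens.

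The window and analysis changes alter no dosing. The cost is slightly tighter scheduling of one visit, two recorded items and a few lines of text. The narrower window does not remove all timing variation: under the assumptions above Day 6 still lies within 0.90 to 1.10 of steady state, which is why the adjustment is kept.
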